10.2 Safety Review

Both the risks listed in Section 4.1 and unknown risks will be monitored as follows:

Research-related risks include bruising and pain at the location of blood draws. Patents will be monitored for these risks at the time of blood draw by the phlebotomist, at each clinic visit (enrollment as well as months 1, 2, 3, and 8) by their primary gastroenterologist, and via phone call (days 14 and 72) by research staff.

10.3 Reporting Plans

The Principal Investigator at BMC/BU Medical Campus will report Unanticipated Problems, safety monitors' reports, and Adverse Events to the BMC/BU Medical Center IRB in accordance with IRB policies:

- Unanticipated Problems occurring at BMC/BU Medical Campus involving a fatal or life-threatening event will be reported to the IRB within 2 days of the investigator learning of the event.
- Unanticipated Problems occurring at BMC/BU Medical Campus not involving a fatal or lifethreatening event will be reported to the IRB within 7 days of the investigator learning of the event.
- Reports from safety monitors with recommended changes will be reported to the IRB within 7 days of the investigator receiving the report.
- Adverse Events (including Serious Adverse Events) will be reported in summary at the time of
 continuing review, along with a statement that the pattern of adverse events, in total, does not
 suggest that the research places subjects or others at a greater risk of harm than was previously
 known.
- Reports from safety monitors with no recommended changes will be reported to the IRB at the time of continuing review.

10.4 Stopping Rules

The study has no stopping rules.

11 Data Handling and Record Keeping

11.1 Confidentiality

All paper-based data will be filed in a locked cabinet for a minimum of 7 years after the end of the study, only accessible to the PI and co-investigators. All electronic information will be stored on a password protected computer in the GI section and numerically coded in a spreadsheet format, only accessible to the PI and co-investigators. Seven years after the completion of the study, all paper-based files will be destroyed by secure means and all computer data will be deleted. All patient data, including demographic information and study assessments, will be securely entered into REDCap, ensuring data confidentiality. Access to the REDCap database will be restricted to authorized research personnel for participant privacy and data protection compliance.

For urgent unanticipated problems, communication of information will occur over secured urgent emails followed by telephone calls among co-investigators and research staff. Among all three sites, scheduled conference calls will be held quarterly (roughly every 3 months) to discuss any interim results or protocol modifications.

The blood samples (coded only with subject ID and to exclude any identifiable private information) will be released outside of the BMC/BU Medical Campus only to co-investigator [name] at the University of Wisconsin School of Medicine and Public Health and will be stored in a locked freezer until the end of the study.

The study's listing on ClinicalTrials.gov will be updated as needed to reflect any future changes in study protocol or results at the completion of the study.

The study monitor or other authorized representatives of the sponsor may inspect all documents and records required to be maintained by the investigator, including but not limited to, medical records (office, clinic, or hospital) and pharmacy records for the subjects in this study. The clinical study site will permit access to such records.

11.2 Source Documents

Source documents include hospital records, clinical and office charts, and laboratory notes.

Data generated by the methods described in the protocol will be recorded in the subjects' medical records and/or study progress notes. Data may be transcribed legibly on CRFs supplied for each subject or directly inputted into an electronic system or any combination thereof.

11.3 Case Report Forms

The study case report form (CRF) will be the primary data collection instrument for the study. All data requested on the CRF will be recorded. All missing data will be explained. If a space on the CRF is left blank because the procedure was not done or the question was not asked, "N/D" will be written. If the item is not applicable to the individual case, "N/A" will be written. All entries will be printed legibly in black ink. If any entry error has been made, to correct such an error, a single straight line will be drawn through the incorrect entry and the correct data will be entered above it. All such changes will be initialed and dated. There will be no erasures or white-out on CRFs. For clarification of illegible or uncertain entries, the clarification will be printed above the item, then initialed and dated. The following source data will be recorded directly on the CRFs: study ID, age, sex, race, subtype of UC, medical and surgical history including vaccinations, medication history, and adverse effects.

See the Appendix for the following CRFs:

- 1. Baseline visit data collection form
- 2. 2-month visit data collection form
- 3. 3-month visit (1-month post-immunization) data collection form
- 4. 8-month visit (6 months post-immunization) data collection form
- 5. Herpes zoster vaccine diary card
- 6. SCCAI form

11.4 Study Records Retention

All paper-based data will be filed in a locked cabinet for a minimum of 7 years after the end of the study, only accessible to the PI and co-investigators. All electronic information will be stored on a password protected computer in the GI section and numerically coded in a spreadsheet format, only accessible to the PI and co-investigators. Seven years after the completion of the study, all paper-based files will be destroyed by secure means and all computer data will be deleted.

Statistical Plan

11.5 Study Hypotheses

Our hypothesis is that at 1-month post-immunization, IBD patients on tofacitinib monotherapy will have a slightly diminished level of VZV-specific CMI from Shingrix compared to non-immunosuppressed IBD patients but that the VZV-specific CMI will be comparable to patients on anti-TNFs alone and superior to patients on combination treatment with a thiopurine.

Additional hypothesis:

At 6 months post-immunization, IBD patients on tofacitinib monotherapy will have a slightly diminished level of VZV-specific CMI from Shingrix compared to non-immunosuppressed IBD patients but that the VZV-specific CMI will be comparable to patients on anti-TNFs alone and superior to patients on combination treatment with a thiopurine.

At 1-month post-immunization, IBD patients on tofacitinib monotherapy will have a slightly diminished varicella antibody concentration from Shingrix compared to non-immunosuppressed IBD patients but that the varicella antibody concentration will be comparable to patients on anti-TNFs alone and superior to patients on combination treatment with a thiopurine.

At 6 months post-immunization, IBD patients on tofacitinib monotherapy will have a slightly diminished varicella antibody concentration from Shingrix compared to non-immunosuppressed IBD patients but that the varicella antibody concentration will be comparable to patients on anti-TNFs alone and superior to patients on combination treatment with a thiopurine.

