4.1 Study Objectives

The primary objective of the study is to determine the immunogenicity of the herpes zoster subunit vaccine in ulcerative colitis patients on tofacitinib monotherapy compared to those on anti-tumor necrosis factor monotherapy, combination treatment with an anti-TNF agent and a thiopurine, and UC patients on 5-aminosalicylates or off therapy. Participants will be receiving the UC treatment regimens as standard of care prior to enrollment into the study. Immunogenicity will be evaluated by measuring humoral and cell mediated immunity in UC patients on tofacitinib who receive the two-dose herpes zoster vaccine. We will evaluate short term immunogenicity at one month after the second vaccination dose and sustained immunogenicity at 6 months post vaccination.

The central hypothesis of this proposal is that UC patients on tofacitinib will mount an adequate response to the Shingrix vaccine. We expect that the response will be slightly diminished compared to non-immunosuppressed IBD patients, comparable to those on anti-TNF monotherapy therapy and superior to those on anti-TNF therapy in combination with a thiopurine.

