term steroids which may affect their immunogenicity to vaccines. Thus, we anticipate that IBD patients on tofacitinib monotherapy will have a slightly diminished response to Shingrix compared to non-immunosuppressed IBD patients (or those on aminosalicylates) but that the response will be comparable to patients on anti-TNFs alone and superior to patients on combination treatment with a thiopurine.

The secondary objectives of the study are to monitor for vaccine-related adverse events and change in UC disease activity throughout the duration of the study in order to obtain other practical information that may help inform providers in clinical decision making regarding the use of Shingrix and/or tofacitinib.

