11.7 Statistical Methods

Summary statistics including the mean, median, SD and range will be presented for continuous variables and N (%) will be presented for categorical variables, overall and by IBD group. Comparisons across groups on baseline demographic and clinical characteristics will be performed using ANOVA for continuous variables and the chi-squared test for categorical variables. Any comparison across groups significant at the p< 0.1 level will be considered for a multivariable-adjusted model for the primary outcome.

For the primary outcome of percent change in cell-mediated immunity from baseline to one-month post-immunization, we will first compare the tofacitinib alone group (Group A) to the non-immunosuppressive group (Group D) using a contrast statement as part of an ANOVA model. Comparisons of Group A with Groups B and C will use the same methodology. The same methodology will be used to compare the secondary outcomes among the four IBD groups in a similar manner. Any imbalances in baseline characteristics will be incorporated into a multivariable regression model to determine the adjusted differences between groups.

Incidence of adverse events will also be compared between groups using the chi-squared or Fisher's Exact test, as appropriate. A value of p< 0.05 is considered statistically significant, except where otherwise noted.

12 Ethics/Protection of Human Subjects

This study is to be conducted according to applicable US federal regulations and institutional policies (which are based in federal regulations, guidance, and ICH Good Clinical Practice guidelines).

This protocol and any amendments will be submitted to the Boston Medical Center and Boston University Medical Campus IRB, for formal approval of the study conduct. The decision of the IRB concerning the conduct of the study will be made in writing to the investigator. A copy of the initial IRB approval letter will be provided to the sponsor before commencement of this study.

All subjects for this study will be provided a consent form describing this study and providing sufficient information for subjects to make an informed decision about their participation in this study. The consent form will be submitted with the protocol for review and approval by the IRB. The consent of a subject, using the IRB-approved consent form, must be obtained before that subject is submitted to any study procedure. Consent will be documented as required by the IRB.

13 Literature References

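### The hypothesis that tofacitinib is comparable to anti-TNF monotherapy is assessed only by a difference test at p<0.05, with no confidence interval and no criterion for comparability

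*Combined protocol and SAP*

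**What the plan says.** Section 11.5 (Study Hypotheses) makes three claims about Group A: slightly below Group D, comparable to Group B, and superior to Group C. For cell-mediated immunity at 1 month, the primary outcome, the wording is that "VZV-specific CMI will be comparable to patients on anti-TNFs alone and superior to patients on combination treatment with a thiopurine". The same is said at 6 months. For both time points it is also stated that "the varicella antibody concentration will be comparable to patients on anti-TNFs alone". The central hypothesis in section 4.1 likewise expects the response to be "comparable to those on anti-TNF monotherapy therapy and superior to those on anti-TNF therapy in combination with a thiopurine".

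Section 11.7 (Statistical Methods) first compares A with D by a contrast in an ANOVA of percent change in cell-mediated immunity. It then says: "Comparisons of Group A with Groups B and C will use the same methodology". The approach is extended to the secondary outcomes. The decision level is: "A value of p< 0.05 is considered statistically significant, except where otherwise noted". For reporting, "Summary statistics including the mean, median, SD and range will be presented for continuous variables", and baseline imbalances go into a regression model "to determine the adjusted differences between groups". Neither section 11.7 nor any other part of the documents gives a confidence interval, an equivalence or non-inferiority margin, or a definition of comparable.

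**The concern.** One difference test is assigned to three different claims. It suits superiority to C and the direction of the deficit against D. It does not suit comparability with B, because failing to reject zero difference is not evidence that the difference is small. It also cannot show that a deficit against D is slight, since that depends on the upper end of an interval that is not planned.

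A−B is one of three comparisons for the primary outcome and recurs in each secondary immunogenicity hypothesis. If the p-value is the only result set against that hypothesis, a non-significant A−B contrast could be taken as support for it when the data are also compatible with a sizeable difference. The groups are not randomised, so the adjusted difference matters most, and its precision is the one thing a reader could not recover from the planned summaries.

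**Working it through.** **Inputs.** Section 11.6 gives 25 recruited per arm and 20% attrition, hence 25 × 0.80 = 20 per arm and 80 in total. Alpha is 0.05 (section 11.7); sidedness is not stated, so two-sided is assumed. No SD is given, so results are in SD units, assuming equal SDs and approximate normality. Error degrees of freedom for four groups are 4n − 4: 76 with 20 per arm, 96 with 25.

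**The plan's own figure.** Section 11.6 says more than 200 per arm would be needed for a 10% difference, with A versus D as the example. Taking 90% versus 80% and 80% power (both assumed; section 4.1 cites a response above 90% in healthy people):

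n = [1.960 × √(2 × 0.85 × 0.15) + 0.842 × √(0.90 × 0.10 + 0.80 × 0.20)]² / 0.10² ≈ 199 per arm, or 219 with continuity correction.

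The figure is therefore reproduced approximately. It concerns detecting a difference between A and D and does not bear on whether A and B are comparable.

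**Precision of A−B.** Half-width of the 95% interval = t(0.975, df) × √(2/n).

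- 20 per arm: 1.992 × 0.3162 = 0.630 SD
- 25 per arm: 1.985 × 0.2828 = 0.561 SD

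**Chance that the contrast is non-significant**, from the noncentral t with noncentrality d/√(2/n):

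| True difference d | 20 per arm | 25 per arm |
|---|---|---|
| 0.3 SD | 85% | 82% |
| 0.5 SD | 65% | 58% |
| 0.8 SD | 30% | 20% |

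Non-significance is more likely than not for any true difference below 0.63 SD (20 per arm) or 0.56 SD (25 per arm).

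**A−D and the word slightly.** The smallest observed deficit that reaches p<0.05 equals the half-width, and its interval runs from 0 to twice the half-width: 0 to 1.26 SD with 20 per arm, 0 to 1.12 SD with 25. A true deficit of 0.3 SD, an illustrative reading of slight, reaches p<0.05 only 15% or 18% of the time. A significant result shows direction, not that the deficit is small.

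**What a formal comparability test could do.** For two one-sided tests at 0.05, the 90% interval must lie inside the margin. Its half-width is 0.527 SD (20 per arm) or 0.470 SD (25 per arm). By simulation with a true difference of zero, an illustrative margin of 0.5 SD is met about 2% and 10% of the time. For 80% power at that margin, the normal approximation gives n = 2 × [(1.645 + 1.282)/0.5]² ≈ 69 per arm.

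**What a reader could rebuild.** Group means and SDs give a crude two-group interval with half-width 0.640 SD (38 df) or 0.569 SD (48 df). They do not give an interval for the adjusted difference.

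**The case against.** The strongest reply is that the plan has not made the mistake. It nowhere says that p>0.05 will be read as comparable, and section 4.1 uses the word while ranking expectations for the four groups. Sections 3.2, 6.2 and 11.6 call the study a pilot, with its size set by feasibility and its aim exploratory estimation. The planned models yield standard errors anyway, so an interval is a reporting detail. The four statements in section 11.5 are one sentence applied to two outcomes and two times. The SD-unit figures also assume normality, while the outcome is percent change in ELISPOT counts, which low baselines can skew, with wells above 300 spots reported only as over 300 (section 4.2.1).

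Much of this stands. No powered equivalence test is owed, and the figures illustrate small-sample imprecision without predicting this trial's behaviour. The spot ceiling could also hide differences between strong responders. The core point survives. Section 11.5 lists comparability under study hypotheses, the contrast at p<0.05 is the only analysis aimed at it, and that analysis cannot answer it. The estimation aim in section 11.6 strengthens the case for intervals.

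**Conclusion.** The concern holds. The only analysis planned for A−B cannot support the hypothesis stated for A−B, and no interval is planned for any contrast, adjusted or not. With 20 to 25 per arm, a non-significant result would be the more likely outcome up to a true difference of about 0.56 to 0.63 SD, so the p-value says little about similarity. The textual finding is firm. The sizes rest on two-sided testing, equal SDs and approximate normality, and cannot be converted to percent change because the documents give no SD. Given the declared pilot purpose, this should be corrected before analysis, but it is no reason to enlarge or redesign the study.

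**What to change.** In section 11.7:

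- Report A−B and A−D, and A−C for consistency, as estimated differences with 95% confidence intervals, unadjusted and adjusted, on the planned outcome scale.
- State that p≥0.05 for A−B will not be interpreted as comparability.
- State that comparable and slightly are descriptive terms in this pilot, and that no formal comparability conclusion will be drawn unless a justified margin is fixed before assay results are available, for example before the coded samples are released after enrolment (section 9).
- Keep the difference tests for A versus C and for the direction of A versus D.

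The cost is three or four sentences and output from models already planned. There are no new data, visits or patients, and no change of outcome scale. The downside is that the study will probably be unable to claim comparability, which its size already implies.

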11.6 Sample Size Determination

We will recruit a total of 100 subjects, anticipating 25 subjects per study arm. Assuming an attrition rate of 20%, our goal final sample size is 80 subjects, with 20 subjects in each arm.

Power calculations revealed that >200 patients per study arm would be needed to estimate small differences in efficacy, assuming a 10% difference between tofacitinib monotherapy patients and non-immunosuppressed IBD patients for instance. Since there are no previous data on vaccine responses to HZ in IBD patients from which we can calculate power estimates, sample size has been determined by feasibility of recruitment at various sites. Our goal is to perform exploratory data analyses and derive estimates of vaccine response results in this population to power future studies.

11.7 Statistical Methods

Summary statistics including the mean, median, SD and range will be presented for continuous variables and N (%) will be presented for categorical variables, overall and by IBD group. Comparisons across groups on baseline demographic and clinical characteristics will be performed using ANOVA for continuous variables and the chi-squared test for categorical variables. Any comparison across groups significant at the p< 0.1 level will be considered for a multivariable-adjusted model for the primary outcome.

For the primary outcome of percent change in cell-mediated immunity from baseline to one-month post-immunization, we will first compare the tofacitinib alone group (Group A) to the non-immunosuppressive group (Group D) using a contrast statement as part of an ANOVA model. Comparisons of Group A with Groups B and C will use the same methodology. The same methodology will be used to compare the secondary outcomes among the four IBD groups in a similar manner. Any imbalances in baseline characteristics will be incorporated into a multivariable regression model to determine the adjusted differences between groups.

Incidence of adverse events will also be compared between groups using the chi-squared or Fisher's Exact test, as appropriate. A value of p< 0.05 is considered statistically significant, except where otherwise noted.

12 Ethics/Protection of Human Subjects

This study is to be conducted according to applicable US federal regulations and institutional policies (which are based in federal regulations, guidance, and ICH Good Clinical Practice guidelines).

This protocol and any amendments will be submitted to the Boston Medical Center and Boston University Medical Campus IRB, for formal approval of the study conduct. The decision of the IRB concerning the conduct of the study will be made in writing to the investigator. A copy of the initial IRB approval letter will be provided to the sponsor before commencement of this study.

All subjects for this study will be provided a consent form describing this study and providing sufficient information for subjects to make an informed decision about their participation in this study. The consent form will be submitted with the protocol for review and approval by the IRB. The consent of a subject, using the IRB-approved consent form, must be obtained before that subject is submitted to any study procedure. Consent will be documented as required by the IRB.

13 Literature References

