4.2.2 Secondary Outcome Measures

- #1: **Sustained T cell response.** Sustained change in CMI at 6 months will be assessed after receiving a second dose of booster vaccine post-immunization.
- #2: **Change in antibody response.** Antibody response will be measured by the change in VZV antibody concentration from pre-immunization to 1 month post-immunization. VZV antibody concentrations in serum samples will be measured using a commercially available ELISA kit (Abnova, Walnut, CA) according to the manufacturer's instructions. This quantitative VZV antibody concentration will be in addition to the one that may be needed to determine previous varicella infection for study eligibility.
- #3: **Sustained antibody response.** Sustained change in VZV antibody concentration at 6 months after receiving a second dose of booster vaccine post-immunization will be assessed.
- #4: Vaccine adverse effects. Patients will either receive phone calls from study personnel or be evaluated at clinic visits to ascertain vaccine-related adverse effects at months 1, 2, 3 (1 month post-immunization), and 8 (6 months post-immunization). Our study is underpowered to measure differences in adverse effects between groups. Adverse event data will be reported.
- #5: Change in UC disease activity. The SCCAI will be used to measure disease activity. It is a questionnaire with six subscore topics with scores defined by UC signs and symptoms from 0 to 4 for a

range of scores from 0 to 17. Total scores are interpreted as: Remission = score of 0 to 4 points, Mild Activity = score of 5 to 7 points, Moderate Activity = Score of 8 to 16 points, and Severe Activity = Score of > 16 points.

5 Study Design

The clinical trial will be a Phase IV multi-center non-randomized non-blinded observational study. As part of standard of care for this patient population and therefore outside of the study, each participant will be given two doses (0.5ml each) of the Shingrix vaccine, administered intramuscularly according to the following schedule: A first dose at Month 0 followed by a second dose administered anytime between 2 and 6 months later.

The study population will include adult outpatient subjects with UC. The study will compare the immunogenicity and VZV antibody concentrations in the participants who will be stratified into one of 4 arms (each containing 25 subjects) based on their medical regimen, which is also standard of care and will be established outside of the study:

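### The planned SCCAI comparison contrasts Group A with the other vaccinated arms, so it cannot detect worsening common to all arms; no within-patient change with a confidence interval is planned

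*Combined protocol and SAP*

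**What the plan says.** Section 4.1 sets as a secondary objective to "monitor for vaccine-related adverse events and change in UC disease activity throughout the duration of the study". Section 4.2.2 lists it as outcome #5: "Change in UC disease activity. The SCCAI will be used to measure disease activity". That section defines four activity bands, starting "Total scores are interpreted as: Remission = score of 0 to 4 points". The outcome is called a change; it is not called a percent change, and no visit or definition of flare is given.

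Section 11.7 opens its outcome analysis with "For the primary outcome of percent change in cell-mediated immunity from baseline to one-month post-immunization". Group A is compared with Group D "using a contrast statement as part of an ANOVA model", and then with B and C in the same way. For secondary outcomes it adds only "The same methodology will be used to compare the secondary outcomes among the four IBD groups in a similar manner". Adverse events get a chi-squared or Fisher test. Continuous variables are summarised by mean, median, SD and range, and categorical ones by N (%), overall and by group.

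Under section 9 and the schedule of events, the SCCAI is completed at baseline and at about day 60 (up to day 180), day 90 and day 240. Section 5 has every participant receiving both vaccine doses.

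**The concern.** The objective asks what happens to UC activity in patients followed after vaccination. The stated test asks a different question: whether the change differs between tofacitinib and another regimen. If disease activity rose by a similar amount in all four arms, every planned contrast would be centred on zero. A non-significant result could then be read as reassurance, and section 6.2 expects the data may reassure patients and providers about safety.

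The scale is a second difficulty. Percent change is the primary outcome's scale for ELISPOT counts. The SCCAI is a short symptom score that can be 0. The plan does not say whether the percent scale goes with the method.

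**Working it through.** **Inputs.** From 11.6: 25 recruited per arm and 20% attrition, so 25 × 0.80 = 20 analysed per arm and 80 in all. From 11.7: contrasts A-D, A-B and A-C, and significance at 0.05 (two-sided assumed). From 4.2.2: remission is 0 to 4. From 7.1 and 7.2: no minimum SCCAI for entry. The plan gives no SCCAI sample size, power or baseline distribution, so there is no planned figure to reproduce. The simulation settings below are assumptions.

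**1. Shared worsening cancels.** Write the mean change in arm g as c + d(g), with c the part common to all arms. The A-D contrast estimates [c + d(A)] − [c + d(D)] = d(A) − d(D). The common part c drops out, and likewise for A-B and A-C.

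**2. Size, by simulation.** Four arms of 20; 4,000 runs; Poisson baseline scores; a flare adds 5 to 8 points; other patients move by −1 to +1; scores cannot fall below 0. With baseline mean 2 and the same flare rate in every arm:

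| Flare rate, all arms | A-D contrast rejects | Pooled paired change (n = 80) rejects | One-arm paired change (n = 20) rejects |
|---|---|---|---|
| 10% | about 5% | about 90% | about 17% |
| 20% | about 5% | >99% | about 52% |
| 30% | about 5% | 100% | about 84% |

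With no flares, the pooled paired test rejects in 7.5% of runs rather than 5%, because of the floor at 0. Even so, data already being collected can show a shared worsening that the stated contrast cannot.

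**3. The percent scale, if carried over.** Percent change = 100 × (later − baseline) / baseline. For the same rise of 4 points:

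| Baseline | Percent change |
|---|---|
| 0 | no value |
| 1 | 400% |
| 2 | 200% |
| 4 | 100% |
| 8 | 50% |

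The share of patients scoring 0 is not given. If it were 5%, 20% or 40%, then 80 × share = 4, 16 or 32 patients would have no value. With flare rates of 30% in A and 5% in D and baseline means of 1 to 3, the A-D contrast has 64-66% power on absolute change, against 43-51% on percent change with zeros dropped.

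**4. Precision of a band-shift proportion.** The exact 95% limits for k of n are the 2.5% quantile of Beta(k, n − k + 1) and the 97.5% quantile of Beta(k + 1, n − k). For 2 of 20 (10%) they are 1.2% to 31.7%. For 8 of 80 (10%) they are 4.4% to 18.8%. The pooled figure is therefore worth reporting beside the per-arm ones.

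**The case against.** **The percent scale is not required by the text.** Just before the quoted sentence, 11.7 uses the same phrase for the comparisons with B and C, where it means the ANOVA contrast. Outcome #5 says only change. This stands: a reader might infer that the SCCAI analysis is undefined, but the firm statement is that it is undefined at 0 if percent change carries over and otherwise has no stated scale.

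**A mean contrast does not simply average flares away.** A mean can mask them: with 2 of 20 rising by 6 and the rest falling by 1, it is (2 × 6 − 18 × 1)/20 = −0.3. But this complaint does not combine with the one about percent change. Take 25 patients: three go from 2 to 8, five from 9 to an average of 5.4, and 17 stay put. The absolute mean is (3 × 6 − 5 × 3.6)/25 = 0, while the percent mean is (3 × 300 − 5 × 40)/25 = +28%. Nor does a flare proportion have more power between arms: in the 30% versus 5% setting, Fisher's test on new scores of 5 or more had 22-43%, against 64-66% for the absolute-change contrast.

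**The plan is not blind to worsening.** A reader might conclude that it cannot show whether UC worsens. That is too strong. The SCCAI is collected serially, bands are defined, and summaries with median and range by group could reveal flares. The adverse-event definition in 10.1 is wide enough to include a flare, although flare is not named. What these leave out is a stated paired change, its confidence interval, and any use of the bands.

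**The study is exploratory and has no unvaccinated control.** Both are true. No SCCAI analysis here could attribute worsening to the vaccine. But 11.6 makes estimation the goal, and a paired estimate with an interval serves that goal better than a contrast that removes the common change.

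**Conclusion.** The concern holds in this form. The only comparison stated for SCCAI change cannot detect worsening common to the four vaccinated arms, and no within-patient estimate with a confidence interval is planned, although the objective is change over the study. The cancellation follows from the design and needs no assumption. The simulated rates (about 5% for the contrast against about 90% or more for the pooled paired change at flare rates of 10% to 30%) rest on the assumed baseline and flare sizes. The percent-scale problem is conditional on that scale being carried over, and its extent depends on an unknown share of patients scoring 0.

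This is a correction to a fifth secondary outcome in an exploratory study. It does not touch the primary outcome. It is still more than a missing detail, because a better-matched analysis is available from data already collected.

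**What to change.** Add to 11.7, for outcome #5:

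- The absolute paired change in SCCAI points from baseline is reported at each post-baseline visit, per arm and pooled, with 95% CI. Percent change is not used for the SCCAI.
- At the same visits, the number and proportion of patients in a higher SCCAI band than at baseline (bands of 4.2.2) are reported per arm and pooled, with exact 95% CI.
- Contrasts of Group A with D, B and C are on absolute change and are descriptive.
- With no unvaccinated control, these results describe change and do not attribute it to vaccination.

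In the same edit, reconcile the score's maximum. Section 4.2.2 gives a "range of scores from 0 to 17", while the SCCAI form gives 19, which matches its rows: 3 + 2 + 3 + 3 + 4 = 15, plus 1 for each of four listed manifestations.

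The cost is a paragraph of wording and slightly more analysis, with no new visits, data or patients. The band shift is coarse: 4 to 5 counts as worsening and 0 to 4 does not. It is also less sensitive than the mean. The mean in turn has the floor at 0 and can mask a few flares. That is why both are reported.
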